Stanford U19 CCHI. Project 2: Innate and Acquired Immunity to Influenza Infection and Immunization (Under grant 'Adaptive and Innate Immunity, Memory and Repertoire in Vaccination and Infection'); SLVP029.
V2.0_07AUG2015

OHSR	Office for Human Subjects Research
ORA	Office of Regulatory Affairs, DMID, NIAID, NIH, DHHS
PHI	Protected Health Information
PI	Principal Investigator
PK	Pharmacokinetics
QA	Quality Assurance
QC	Quality Control
SAE	Serious Adverse Event/Serious Adverse Experience
SLVP	Stanford-LPCH Vaccine Program
SMC	Safety Monitoring Committee
SOP	Standard Operating Procedure
TIV	Trivalent inactivated influenza vaccine
US	United States
WHO	World Health Organization

PROTOCOL SUMMARY

Title: Project 2: Innate and Acquired Immunity to Influenza Infection and Immunization	
Number of Sites: 1	
Study Duration: 5 years for enrollment, vaccination, analysis	
Subject Participation Duration: 4-5 weeks	
Description of Agent or Intervention: Quadrivalent, Live Attenuated Influenza Vaccine (LAIV4) Quadrivalent, Inactivated Influenza Vaccine (IIV4)	
Objectives:	
Primary:
 
 1. To compare the nasal mucosal transcriptional responses to LAIV4 between the following age groups: 2-4 year old children, 9-13 year old children, and 18-49 year old adults 2. To compare the B cell response to LAIV4 between the following age groups: 2-4 year old children, 9-13 year old children, and 18-49 year old adults 3. To investigate the evolution of B cell repertoire in young children after repeated LAIV4 immunization 4. To compare the B cell response to IIV between the following age groups: 6-23 month old children, 9-13 year old children, and 18-49 year old adults 5. To investigate the evolution of B cell repertoire in young children first immunized with IIV followed by repeated LAIV4 immunization. 
Secondary:
 
 1. To compare the B cell repertoire in response to LAIV4 versus IIV in different age groups.

Description of Study Design: This is a Phase IV study of healthy children and adults who will receive the current seasonal influenza vaccine. There are no exclusions for gender, ethnicity or race. The volunteers will be enrolled into one of 7 groups over a 5-year period. Immunization will be at Day 0. Blood and NP swab samples will be collected at various time points based upon group assignment for various immunological assays.

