5.2 Subject Exclusion Criteria for Enrollment and Subsequent Annual Vaccinations

1. Prior off-study vaccination with the current year's seasonal influenza vaccine
2. Receipt of LAIV in the prior season (does not apply to Groups F and G)
3. Received flu immunizations in 2 or more prior flu seasons (does not apply to Groups F and G)
4. Allergy to egg or egg products, or to vaccine components, including gentamicin, gelatin, arginine or MSG (if will be given LAIV4)
5. Life-threatening reactions to previous influenza vaccinations
6. Asthma in adults. Children aged 2 through 4 years who have asthma or who have had a wheezing episode noted in the medical record within the past 12 months, or for whom parents report that a health care provider stated that they had wheezing or asthma within the last 12 months [If yes, not eligible for LAIV Groups A, B, C, & F].
7. Active systemic or serious concurrent illness, including febrile illness on the day of vaccination
8. History of immunodeficiency (including HIV infection)
9. For children or adolescents through 17 years of age: receiving aspirin therapy or aspirin-containing products [If yes, not eligible for LAIV Groups A, B, C, and F].
10. Known or suspected impairment of immunologic function, including, but not limited to, clinically significant liver disease, diabetes mellitus treated with insulin, moderate to severe renal disease, or any other chronic disorder which, in the opinion of the investigator, might jeopardize volunteer safety or compliance with the protocol.
11. Blood pressure >150 systolic or >95 diastolic at first study visit and the day of vaccination (for children 12 yrs and older, and adults).
12. Hospitalization in the past year for congestive heart failure or emphysema.
13. Chronic Hepatitis B or C
14. Recent or current use of immunosuppressive medication, including systemic glucocorticoids (corticosteroid nasal sprays and topical steroids are permissible in all groups; inhaled steroid use is not permissible)
15. Persons who care for severely immunosuppressed persons who require a protective environment should not receive LAIV, or should avoid contact with such persons for

- 7 days after receipt, given the theoretical risk for transmission of the live attenuated vaccine virus to close contacts. [If yes, may be ineligible for Groups A,B, C and F].

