7 STUDY SCHEDULE

7.1 Screening

Volunteers will be contacted by phone prior to the first study visit. Study staff will briefly review the eligibility criteria, participant availability and the study procedures. If the participant is eligible and interested, the volunteers will be assigned to groups based on, age, inclusion exclusion criteria and availability for annual return vs single year participation.

7.2 Day 0; Enrollment/Baseline/Immunization for all Groups; annually for Groups A and D.

- Adult participants or parents of the volunteer will be provided with a verbal description of the study (purpose and study schedule and procedures). They then will be asked for any questions and to read/sign the consent form (in the first year only). Minor children ages 7-17 years will be given an assent at enrollment. The consent form will be signed prior to the performance of any study procedures. The study staff will discuss with the volunteer or volunteer's parent of their study eligibility criteria and concomitant medication use.
- Obtain vital signs (oral temperature, pulse, and respiratory rate), height and weight. Obtain blood pressure for volunteers 12 years and older.
- Collect blood samples (**except Group C**) as follows:

For blood volumes ≥ 20 mL, collect one 5 mL gold top tube (serum), one 2.5 mL PAXgene tube and one 2.5 mL heparinized, green top tube (CyTOF sample). The remainder of the blood sample will be collected in heparinized, green top tubes. Blood volumes <20 mL will be collected in heparinized, green top tubes only.

- For children weighing more than 100 lb., and from adults, total volume not to exceed 70 mL
 - From children weighing 66-100 lb: total volume not to exceed 30 mL
 - From children weighing 61-65 lb: total volume not to exceed 25 mL
 - From children weighing 41-60 lbs: total volume not to exceed 20 mL
 - From children weighing 16-40 lbs: total volume not to exceed 10 mL
 - From children 6 months through 35 months old, regardless of weight: Obtain a 4 mL blood sample into a heparin (green top) tube.
- All volunteers will be administered the seasonal flu vaccine according to the group assignment. Unless there is a different recommendation from the ACIP in a given year, Group A, B, C and F will receive intranasal spray of LAIV4. Group D, E and G

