will be vaccinated with IIV4. Children who are vaccine-naïve will receive their Dose 1 of their vaccine at this visit. Volunteers will be observed in clinic for 15 minutes for any immediate serious reactions. Vaccine-naïve volunteers requiring Dose 2 will return at least 28 days post-Dose 1.

- A Memory Aid will be given to the volunteers/volunteer's parent with written and oral instructions for collection of information about serious adverse events. The memory aid is a simple diary for volunteer to record change in a health status and medications between study visits.
- The schedule for subsequent study visits will be reviewed.

7.3 Day 1 post- Dose 1 immunization for Group C and Group F only

- Review of medications and memory aid for serious adverse events
- Collect nasopharyngeal swab specimen; no blood sample will be collected at this visit.
- The schedule for subsequent study visits will be reviewed.

7.4 Day 6-8 post-Dose 1 immunization except Group C and vaccine-naïve volunteers in Group D and Group E requiring Dose 2; annually for Groups A and D.

- Review of medications and memory aid for serious adverse events
- Collect blood samples as follows:

All blood samples will be collected in heparinized, green top tubes to be picked up by the [name] lab for processing and analysis. For sample volumes >30 mL, one heparinized, green top tube will be sent to the HIMC if available ([name] lab requires at least 30 mL in heparinized, green top tubes at Day 6-8).

- For children weighing more than 100 lb., and from adults: total volume not to exceed 70 mL
 - From children weighing 66-100 lb: total volume not to exceed 30 mL
 - From children weighing 61-65 lb: total volume not to exceed 25 mL
 - From children weighing 41-60 lbs: total volume not to exceed 20 mL
 - From children weighing 16-40 lbs: total volume not to exceed 10 mL
 - From children 6 months through 35 months old, regardless of weight: Obtain a 4 mL blood sample into a heparin (green top) tube.
- The schedule for subsequent study visits will be reviewed for, Group F and G

- This will be the final visit for volunteers with prior influenza vaccination history in Group A, B, D and E. Complete Study Status form and Study Reimbursement form for these volunteers.

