Appendix A. Schedule of visits

Appendix B. Schedule of events

Appendix C. Season-specific FluMist Quadrivalent package inserts 2014-2018

Appendix D. Season-specific Fluzone Quadrivalent package insert 2014-2018

APPENDIX A: SCHEDULE OF VISITS

Groups	Naïve /prior vacc	Day 0	Day 1 Post-Dose 1	Day 6-8 Post-Dose1	Day 21 Post-Dose1	Day 28-32 post-Dose 1 (for Dose 2) Day 28 ± 4 Post-Dose 1 (blood draw, NP Swab)	Day 6-8 Post-Dose 2
Group A 2-4 yo Annuals	naive	LAIV4 Dose 1/ Blood	--	Blood	--	LAIV4 Dose 2	--
	Prior vacc	LAIV4/Blood	--	Blood	--	--	--
Group B 2-4 yo Single yr	Naive	LAIV4 Dose 1/ Blood,	--	Blood	--	LAIV4 Dose 2	--
	Prior vacc	LAIV4/Blood	--	Blood	--	--	--
Group C 2-4 yo Single yr	Naive	LAIV4 Dose 1	NP Swab	--	NP Swab	LAIV4 Dose 2	--
	Prior vacc	LAIV4	NP Swab	--	NP Swab	--	--
Group D 6-23mo Annual	Naive	IIV4* Dose 1/ Blood	--	--	--	IIV4* Dose 2	Blood
	Prior vacc	IIV4*/ Blood	--	Blood	--	--	--
Group E 6-23mo Single yr	Naive	IIV4 Dose 1/ Blood	--	--	--	IIV4 Dose 2	Blood
	Prior vacc	IIV4/ Blood	--	Blood	--	--	--
Group F 9-13 yo 18-49 yo	Prior vacc	LAIV4, blood	NP Swab	Blood	--	Blood, NP Swab	--
Group G 9-13 yo 18-49 yo	Prior vacc	IIV4, blood	--	Blood	--	Blood	--

* When these children turn 2 yrs old in annual f/u, they will be switched to receive LAIV4 vaccine unless they develop a contraindication.

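### Section 7.2 and the Appendix A footnote give different vaccines for Group D annual returns at 24 months or older, and the Section 5.2 exclusions fit neither the switch to LAIV4 nor its repetition

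*Combined protocol and SAP*

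**What the plan says.** Section 7.2 describes the Day 0 visit, and its heading gives the scope as "Enrollment/Baseline/Immunization for all Groups; annually for Groups A and D". The vaccine bullet reads "Group A, B, C and F will receive intranasal spray of LAIV4. Group D, E and G" and continues over the page: "will be vaccinated with IIV4". An exception for a differing ACIP recommendation opens the LAIV4 sentence. The section has no age rule and does not point to Appendix A.

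Appendix A puts an asterisk on the IIV4 entries for Group D, in both the naïve and the previously vaccinated rows, and not on those for Group E. The footnote is: "When these children turn 2 yrs old in annual f/u, they will be switched to receive LAIV4 vaccine unless they develop a contraindication".

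The Group D descriptions in the Protocol Summary and Section 4 ask the children back yearly. The Summary adds that this follows ACIP guidelines. Neither names the product for those returns.

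Summary primary objective 5 is: "To investigate the evolution of B cell repertoire in young children first immunized with IIV followed by repeated LAIV4 immunization". Section 3.1 has no such primary objective. Its nearest match is secondary objective 2, which refers to different vaccine types without stating an order.

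The heading of Section 5.2 applies its exclusions both at enrolment and at later annual vaccinations. The bracket on exclusion 6 (asthma or wheeze) says "not eligible for LAIV Groups A, B, C, & F". The brackets on exclusions 9 (aspirin), 15 (carers of severely immunosuppressed people) and 20 (influenza antivirals) list the same four groups. Exclusion 4 (allergy) is tied to receiving LAIV4 and names no group. Exclusions 2 (LAIV the season before) and 3 (vaccinated in two or more earlier seasons) exempt only Groups F and G.

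**The concern.** Group D is the only group designed to move from IIV4 to LAIV4 within the study, so objective 5 depends on it. Staff working from Section 7.2 would give IIV4 at each return, and the sequence would not arise. Staff working from the footnote would give LAIV4 to children whom four group-specific screening brackets do not mention. Section 10.3 compares repertoires between vaccines, so which product a child received in which season decides what the Group D data can be used for. With at most six children, one or two handled under the other rule would be a large share of the group.

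**Working it through.** There is no figure in the plan to reproduce. Section 10.2 gives 20 per age group by precedent, with no alpha, power, effect size or SD. The check compares passages and counts seasons.

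**1. Product at a Group D return at 24 months or older**
- Section 7.2 (heading plus vaccine bullet): IIV4.
- Appendix A footnote: LAIV4, unless contraindicated.
- Summary and Section 4: no product named.

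The conflict is between two places; the other two are silent.

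**2. LAIV4 seasons available**

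Inputs: entry age a = 6 to 23 months (Section 4) and five enrolment seasons (Summary). Assumptions: returns exactly 12 months apart, no visits after season 5, no contraindication and no ACIP override. Age at return k is a + 12k. For enrolment in season s, k runs from 0 to 5 − s. The footnote gives LAIV4 when a + 12k ≥ 24.
- a = 12-23: the condition holds from k = 1 (ages 24-35 months), giving 5 − s LAIV4 seasons.
- a = 6-11: at k = 1 the age is 18-23 months, so the condition holds from k = 2 (ages 30-35 months), giving max(0, 4 − s).

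| Enrolment season | 1 | 2 | 3 | 4 | 5 |
|---|---|---|---|---|---|
| Footnote, entry 12-23 months | 4 | 3 | 2 | 1 | 0 |
| Footnote, entry 6-11 months | 3 | 2 | 1 | 0 | 0 |
| Section 7.2 read literally, any entry age | 0 | 0 | 0 | 0 | 0 |

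Taking repeated to mean at least two LAIV4 seasons, the footnote supplies it only for enrolment by season 3 (5 − 3 = 2) or season 2 (4 − 2 = 2) respectively.

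**3. Sensitivity to visit spacing**

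Enrolment runs August to December. If returns fall in the same window (an assumption), consecutive visits are about 8 to 16 months apart. Entry at 12 months in December with return in August gives 12 + 8 = 20 months, so no switch yet. Entry at 11 months in August with return in December of the next year gives 11 + 16 = 27 months, so a switch at the first return. The 12-month split is therefore approximate.

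**4. Exclusions 2 and 3 applied to the footnote sequence, counting in-study doses, child naïve at entry**
- Entry 12-23 months: season 1 IIV4; season 2 LAIV4 is allowed (one earlier season); season 3 is barred by both exclusions. One LAIV4 season.
- Entry 6-11 months: seasons 1 and 2 IIV4; season 3 is barred by exclusion 3 (two earlier seasons). No LAIV4 season.
- Inclusion 6 also admits children with one earlier IIV season. They would reach 1 + 1 = 2 earlier seasons at the first return and be barred there.

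So under a literal reading repeated LAIV4 cannot occur in Group D even if the footnote is followed. The text does not exempt in-study doses.

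**5. Screening for LAIV4 under the footnote**

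Exclusions 6, 9, 15 and 20 carry brackets that omit Group D. Exclusion 4 covers Group D by product. The footnote's contraindication clause is general and not linked to the listed criteria.

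**The case against.** The footnote is an explicit rule, marked on Group D only, and it matches Summary objective 5. Section 7.2 does not itself say that IIV4 is given at every return: that follows from joining a multi-group heading to a bullet that also serves enrolment. The bullet refers to group assignment, and Appendix A is the group-by-group schedule. This stands, and it rules out a stronger reading that a reader might reach, namely that the vaccine sequence or the objective is undefined. A sequence can be derived from the footnote, and the objective is stated, although at different levels and in different wording in the Summary and Section 3.1. The two passages still give different products for the same visit, and nothing says which prevails.

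A reader might also infer that all six children are affected. The plan says up to six, and late enrollees may never reach a return at 24 months within the study seasons.

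Nor do the documents show that a mix of sequences would be uninterpretable. Section 10.3 builds repertoires from sequence data, and a child whose vaccine history is known remains informative individually. Sections 6.3 and 6.4 already have vaccine units and vaccinations recorded.

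Finally, it would be too much to say that Group D has no LAIV screening. Exclusion 4 applies by product, and several general exclusions apply to every group. The gap is confined to the four brackets.

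**Conclusion.** The point holds as an internal inconsistency. For Group D returns at 24 months or older, Section 7.2 and the Appendix A footnote name different vaccines. Under Section 7.2 as written, Group D yields 0 LAIV4 seasons and nothing for Summary primary objective 5. Under the footnote it yields between 0 and 4 per child, depending on entry age and enrolment season, but the brackets on four exclusions do not cover the group, and exclusions 2 and 3 read literally reduce the count to at most 1.

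The size is limited: up to six children, only those who return at 24 months or older, in a study that Section 10.1 calls exploratory. The counts assume 12-month spacing and five study seasons; the result for exclusions 2 and 3 also assumes that in-study doses count. The conflict itself rests on none of these assumptions. It is worth correcting because it determines which product is given and whether a stated objective can be addressed.

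**What to change.** Reconcile the following so that all give the same annual vaccine and the same screening for Group D and agree with the objective:
- the Section 7.2 vaccine bullet and the Appendix A footnote, with a cross-reference between them;
- the Group D text in the Summary and Section 4, naming the product at annual returns;
- the group brackets on exclusions 6, 9, 15 and 20;
- exclusions 2 and 3, stating whether in-study doses count at annual visits;
- Summary primary objective 5 and Section 3.1 secondary objective 2, which differ in level and wording.

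Add a sentence to Section 10.3 that Group D is analysed by the vaccine actually received in each season, with each child's sequence listed. Which vaccine rule and which screening apply is for the investigators and sponsor to decide.

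The cost is protocol wording in these places and the usual amendment review. No new data collection is needed, since vaccinations are already recorded, and no sample-size figure changes.

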APPENDIX B: SCHEDULE OF EVENTS

	Day 0	Day 1	Day 6-8 post-Dose 1	Day 21 post- Dose 1	Day 28-32 post- Dose 1 (give Dose 2) OR Day 24 - 32 Post-Dose 1 (blood draw)	Day 6-8 post-Dose 2
Obtain Informed Consent/Assent	X					
Eligibility	X					
Concomitant meds	X		X		X	
Vital Signs ¹	X		X ²		X ²	
Blood Draw	X		X		X ⁷	X ⁶
NP Swab		X ^{3, 4}		X ³	X ⁴	
Immunization	X				X ⁵	
Clinical Assessment	X ²	X ²	X ²	X ²	X ²	X ²
Review of SAEs	X	X	X	X	X	X

¹ Vital Signs: temperature, pulse, respiration; height and weight (blood pressure for adolescents as indicated and adults)

² As indicated

³ Group C only

⁴ Group F only

⁵ Dose 2 vaccine (at least 28 days post-Dose 1), Vaccine-naïve volunteers in Groups A-E only

⁶ Groups D and E vaccine-naïve volunteers only

⁷ Groups F and G volunteers only

APPENDIX C: FLUMIST QUADRIVALENT PACKAGE INSERTS 2014-2018

Attached in eProtocol section 16

APPENDIX D: FLUZONE QUADRIVALENT PACKAGE INSERTS 2014-2018

Attached in eProtocol section 16
